8.3.5.2. Exposure During Breastfeeding

An exposure during breastfeeding occurs if:

- A female is found to be breastfeeding while being exposed or having been exposed to study intervention (ie, environmental exposure). An example of environmental exposure during breastfeeding is a female family member or healthcare provider who reports that she is breastfeeding after having been exposed to the study intervention by inhalation or skin contact.

The investigator must report exposure during breastfeeding to Pfizer Safety within 24 hours of the investigator's awareness, irrespective of whether an SAE has occurred. The information must be reported using the CT SAE Report Form. When exposure during breastfeeding occurs in the setting of environmental exposure, the exposure information does not pertain to the participant enrolled in the study, so the information is not recorded on a CRF. However, a copy of the completed CT SAE Report Form is maintained in the investigator site file.

An exposure during breastfeeding report is not created when a Pfizer drug specifically approved for use in breastfeeding women (eg, vitamins) is administered in accord with authorized use. However, if the infant experiences an SAE associated with such a drug, the SAE is reported together with the exposure during breastfeeding.

8.3.5.3. Occupational Exposure

An occupational exposure occurs when, during the performance of job duties, a person (whether a healthcare professional or otherwise) gets in unplanned direct contact with the product, which may or may not lead to the occurrence of an AE.

The investigator must report occupational exposure to Pfizer Safety within 24 hours of the investigator's awareness, using the CT SAE Report Form, regardless of whether there is an associated SAE. Since the information does not pertain to a participant enrolled in the study, the information is not recorded on a CRF; however, a copy of the completed CT SAE Report Form is maintained in the investigator site file.

8.3.6. Cardiovascular and Death Events

Not applicable.

8.3.7. Disease-Related Events and/or Disease-Related Outcomes Not Qualifying as AEs or SAEs

Not applicable.

8.3.8. Adverse Events of Special Interest

All adverse events of special interest (AESIs) must be reported as an AE or SAE following the procedures described in [Section 10.3](#). An AESI is to be recorded as an AE or SAE on the CRF. In addition, an AESI that is also an SAE must be reported using the CT SAE Report Form.

8.3.8.1. Lack of Efficacy

This section is not applicable because efficacy is not expected in the study population.

8.3.9. Medical Device Deficiencies

Not applicable.

8.3.10. Medication Errors

Medication errors may result from the administration or consumption of the investigational product by the wrong participant, or at the wrong time, or at the wrong dosage strength, or noncompliance as described in [Section 6.4](#).

Exposures to the investigational product under study may occur in clinical trial settings, such as medication errors.

Safety Event	Recorded on the CRF	Reported on the CT SAE Report Form to Pfizer Safety Within 24 Hours of Awareness
Medication errors	All (regardless of whether associated with an AE)	Only if associated with an SAE

Medication errors include:

- Medication errors involving participant exposure to the investigational product;
- Potential medication errors or uses outside of what is foreseen in the protocol that do or do not involve the study participant.

Such medication errors occurring to a study participant are to be captured on the medication error page of the CRF, which is a specific version of the AE page.

In the event of a medication dosing error, the Sponsor should be notified within 24 hours.

Whether or not the medication error is accompanied by an AE, as determined by the investigator, the medication error is recorded on the medication error page of the CRF and, if applicable, any associated AE(s), serious and nonserious, are recorded on an AE page of the CRF.

Medication errors should be reported to Pfizer Safety within 24 hours on a CT SAE Report Form **only when associated with an SAE**.

8.4. Treatment of Overdose

For this study, any dose of investigational product greater than that prescribed at each dose level will be considered an overdose.

Sponsor does not recommend specific treatment for an overdose.

In the event of an overdose, the investigator should:

1. Contact the medical monitor within 24 hours.
2. Closely monitor the participant for any AEs/SAEs and laboratory abnormalities for at least 5 half-lives or 28 calendar days after the overdose of PF-06755347 (whichever is longer).
3. Obtain a blood sample for PK analysis within 2 days from the date of the last dose of study intervention if requested by the medical monitor (determined on a case-by-case basis).

4. Document the quantity of the excess dose as well as the duration of the overdose in the CRF.
5. Overdose is reportable to Safety **only when associated with an SAE**.

Decisions regarding dose interruptions or modifications will be made by the investigator in consultation with the medical monitor based on the clinical evaluation of the participant.

8.5. Pharmacokinetics

8.5.1. Analysis of PF-06755347

Blood samples (2 mL) to provide approximately 0.5 mL plasma for pharmacokinetic analysis will be collected into appropriately labeled tubes containing dipotassium ethylene diamine tetraacetic acid (K₂EDTA) at times specified in the [SoA](#).

The actual times may change but the number of samples will remain the same. All efforts will be made to obtain the pharmacokinetic samples at the exact nominal time relative to dosing. However, samples obtained within 10% of the nominal time (eg, within 6 minutes of a 60 minute sample) from dosing will not be captured as a protocol deviation, as long as the exact time of the sample collection is noted on the source document and data collection tool (eg, DCT). Collection of samples more than 10 hours after dose administration that are obtained ≤1 hour away from the nominal time relative to dosing will not be captured as a protocol deviation, as long as the exact time of the collection is noted on the source document and data collection tool (eg, DCT). This protocol deviation window does not apply to samples to be collected more than 10 hours after dose administration at outpatient/follow-up visits with visit windows.

Samples will be analyzed using a validated analytical method in compliance with Pfizer standard operating procedures.

The PK samples must be processed and shipped as indicated in the instructions provided to the investigator site to maintain sample integrity. Any deviations from the PK sample handling procedure (eg, sample collection and processing steps, interim storage or shipping conditions), including any actions taken, must be documented and reported to the Sponsor. On a case-by-case basis, the Sponsor may make a determination as to whether sample integrity has been compromised. Any deviation from the specified sample handling procedure resulted in compromised sample integrity will be considered a protocol deviation.

As part of understanding the pharmacokinetics of the IP, samples may be used for metabolite identification and/or evaluation of the bioanalytical method, **CCI** [REDACTED]. [REDACTED] These data will not be included in the clinical study report (CSR).

8.5.2. Analysis of Anti-Drug Antibodies

Blood samples (4 mL) to provide approximately 1.5 mL serum for the assessment of antidrug (anti-PF-06755347) antibodies will be collected into appropriately labeled tubes containing no anticoagulant or gel serum separator at visits specified in the [SoA](#).

The ADA sample analysis will follow a tiered approach of screening, confirmation, and titer determination. Samples will be analyzed using a validated analytical method in compliance with Pfizer standard operating procedures.

The ADA samples must be processed and shipped as indicated in the instructions provided to the investigator site to maintain sample integrity. Any deviations from the immunogenicity sample handling procedure (eg, sample collection and processing steps, interim storage or shipping conditions), including any actions taken, must be documented and reported to the Sponsor. On a case-by-case basis, the Sponsor may make a determination as to whether sample integrity has been compromised. Any deviation from the specified sample handling procedure resulting in compromised sample integrity will be considered a protocol deviation.

CCI [REDACTED]

CCI [REDACTED]

[REDACTED]

[REDACTED]

[REDACTED]

[REDACTED]

[REDACTED]

[REDACTED]

CCI [REDACTED]

[REDACTED]

[REDACTED]

[REDACTED]

[REDACTED]

[REDACTED]

[REDACTED]

[REDACTED]

[REDACTED]

[REDACTED]

[REDACTED]

[REDACTED]

[REDACTED]

[REDACTED]

[REDACTED]

CCI

[Redacted]

[Redacted]

[Redacted]

[Redacted]

[Redacted]

[Redacted]

[Redacted]

[Redacted]

CCI

[Redacted]

CCI [REDACTED]

[REDACTED]	[REDACTED]	[REDACTED]	[REDACTED]	[REDACTED]
[REDACTED]	[REDACTED]	[REDACTED]	[REDACTED]	[REDACTED]
[REDACTED]	[REDACTED]	[REDACTED]	[REDACTED]	[REDACTED]
[REDACTED]	[REDACTED]	[REDACTED]	[REDACTED]	[REDACTED]
[REDACTED]	[REDACTED]	[REDACTED]	[REDACTED]	[REDACTED]
[REDACTED]	[REDACTED]	[REDACTED]	[REDACTED]	[REDACTED]
[REDACTED]	[REDACTED]	[REDACTED]	[REDACTED]	[REDACTED]
[REDACTED]	[REDACTED]	[REDACTED]	[REDACTED]	[REDACTED]
[REDACTED]	[REDACTED]	[REDACTED]	[REDACTED]	[REDACTED]
[REDACTED]	[REDACTED]	[REDACTED]	[REDACTED]	[REDACTED]
[REDACTED]	[REDACTED]	[REDACTED]	[REDACTED]	[REDACTED]
[REDACTED]	[REDACTED]	[REDACTED]	[REDACTED]	[REDACTED]
[REDACTED]	[REDACTED]	[REDACTED]	[REDACTED]	[REDACTED]
[REDACTED]	[REDACTED]	[REDACTED]	[REDACTED]	[REDACTED]
[REDACTED]	[REDACTED]	[REDACTED]	[REDACTED]	[REDACTED]

9. STATISTICAL CONSIDERATIONS

Detailed methodology for summary and statistical analyses of the data collected in this study is outlined here and further detailed in a statistical analysis plan (SAP), which will be maintained by the Sponsor. The SAP may modify what is outlined in the protocol where appropriate; however, any major modifications of the primary endpoint definitions or their analyses will also be reflected in a protocol amendment.

9.1. Statistical Hypotheses

No formal statistical hypothesis testing will be performed in this study.

9.2. Sample Size Determination

No formal sample size calculation was performed. For cohorts that include healthy participants, cohort size of approximately 4 (3 active, 1 placebo) to 8 (4 active, 2 placebo) participants has been chosen to ensure appropriate sample size to provide adequate safety, toleration and PK information at each dose level and to provide a placebo comparison group, while minimizing exposure to humans of a new biologic entity. ITP Cohorts will not include placebo. ITP cohort size will be approximately 3 to 6 participants to reflect the number dosed receiving PF-06755347 in HP cohorts. Participants who discontinue during the trial may be replaced at the discretion of the Sponsor and Investigator.

9.3. Populations for Analysis

For purposes of analysis, the following populations are defined:

Population	Description
Enrolled	All participants who sign the ICD.
PK Population	The PK concentration population is defined as randomized participants who received at least one dose and have at least 1 concentration. The PK parameter analysis population is defined as all randomized participants who received at least one dose and have at least 1 of the PK parameters of interest.
PD Population	The PD analysis population is defined as all randomized participants treated who have at least one PD assessment in at least one cohort.
Safety	All participants randomly assigned to investigational product and who receive at least 1 dose of investigational product. Participants will be analyzed according to the product they actually received.

9.4. Statistical Analyses

The SAP will be developed and finalized before database lock and will describe the participant populations to be included in the analyses, and procedures for accounting for missing, unused, and spurious data. This section is a summary of the planned statistical analyses of the primary and secondary endpoints.

9.4.1. Efficacy Analyses

An efficacy analysis is not applicable to this study.

9.5. Pharmacokinetic Analysis

9.5.1. Derivation of Pharmacokinetic Parameters

PK parameters following single dose administration will be derived from the plasma PF-06755347 concentration-time profiles as defined in [Table 10](#) for each participant and treatment, as applicable, using noncompartmental analysis of concentration-time data. Samples below the lower limit of quantitation will be set to zero for analysis. Actual sample collection times will be used for the pharmacokinetic analysis.

Table 10. Plasma Pharmacokinetic Parameter Definition

Parameter	Definition	Mode of Determination
C_{max}	Maximum plasma concentration	Observed directly from data
C_{max} (dn)	Dose normalized C_{max}	$C_{max}/Dose$
T_{max}	Time for C_{max}	Observed directly from data as time of first occurrence
AUC_{last}	Area under the plasma concentration-time profile from time zero to the time of last quantifiable concentration (C_{last})	Linear/Log trapezoidal method
AUC_{last} (dn)	Dose normalized AUC_{last}	$AUC_{last}/Dose$
AUC_{inf}^a	Area under the plasma concentration-time profile from time zero extrapolated to infinite time	$AUC_{last} + (C_{last}^*/k_{el})$, where C_{last}^* is the predicted plasma concentration at the last quantifiable time point estimated from the log-linear regression analysis
AUC_{inf} (dn) ^a	Dose normalized AUC_{inf}	$AUC_{inf}/Dose$
$t_{1/2}^a$	Terminal half-life	$\text{Log}_e(2)/k_{el}$, where k_{el} is the terminal phase rate constant calculated by a linear regression of the log-linear concentration-time curve. Only those data points judged to describe the terminal log-linear decline will be used in the regression.
CL (IV) ^a	Systemic Clearance	$Dose/AUC_{inf}$
V_{ss} (IV) ^a	Volume of distribution at steady-state	$CL * MRT$ where $MRT = (AUMC_{inf}/AUC_{inf}) - (DOI/2)$
CL/F (SC)	Apparent clearance	$Dose/AUC_{inf}$ for SC route
V_z/F (SC)	Apparent volume of distribution	$Dose / (AUC_{inf} * k_{el})$ for SC route
F (SC)	bioavailability	$F = AUC_{inf,sc} / AUC_{inf,iv}$

a. If data permit.

Abbreviation: AUMC = area under the first moment plasma concentration curve; dn=dose normalized to a 1 mg dose; DOI = duration of infusion; MRT = mean residence time.

Actual PK sampling times will be used in derivation of PK parameters.

The supporting data from the estimation of $t_{1/2}$ will also be reported: the terminal phase rate constant (k_{el}); the first, last, and number of time points used for the log-linear regression ($k_{el,t(lo)}$, $k_{el,t(hi)}$, and $k_{el,t(n)}$); the goodness-of-fit statistic from the regression (r^2); and the percent of the area under the plasma concentration-time curve from time zero to infinite time, AUC_{inf} , obtained by forward extrapolation ($AUC_{extrap}\%$).

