Dose escalation beyond the starting dose will be dictated by the criteria summarized in [Section 6.7](#) and will aim to occur in incremental increases of no more than half-log (ie, 3.3 fold) based on predicted exposure, with smaller increments if required due to emerging safety data or once the expected PF-06755347 exposure approaches the PK stopping limit. The actual doses to be evaluated in the escalation sequence as well as the number of dose levels to be evaluated may be adjusted according to emerging safety, tolerability and PK data, provided the dose escalation criteria specified in [Section 6.6](#) and [Section 6.7](#) are not violated. These criteria are applicable to both IV and SC administration.

A body weight-based dosing approach (mg/kg) was used in this study for the IV cohorts with the goal of reducing inter-individual variations in IV infusion/dosing rate and PK exposure. PF-06755347 was administered as a single infusion over 60 minutes for the starting dose of 0.01 mg/kg. Based on emerging safety data of cytokine elevation at the 1 mg/kg dose level, the infusion duration was increased to 3 hours for an expansion cohort at 1 mg/kg. ([Section 6.1.1.1](#)). The increase in infusion duration was expected to modulate the tolerability of PF-06755347. Safety data from the 1 mg/kg expansion cohort showed that an increase in

infusion duration to 3 hours did not modulate the tolerability profile of PF-06755347 and subsequently, the next cohort used 0.7 mg/kg infused over 1 hour. Guidelines for the proposed infusion rate at each dose level are provided in [Section 6.1.1.1](#). However, the actual dosing rate could have been reduced and/or the overall infusion time increased at the discretion of the PI and upon the review of the available safety data. The overall infusion time was not to exceed 4 hrs. If deemed appropriate by the PI, concomitant medications (such as acetaminophen and diphenhydramine) coupled with adjustment of dosing rate could have been implemented to manage possible emerging symptoms that may have been related to transient pro-inflammatory activity.

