4.2.1.3.2. Subcutaneous Administration in Healthy Participants

Following IV administration of PF-06755347, the observed safety data to date has shown Grades 1 and 2 CRS associated with IV doses of 1.0 and 0.7 mg/kg, respectively. Cytokine (eg, IL-6) elevation peaked within the first few hours following IV administration and returned to baseline levels within 24 hours. These results may suggest that the degree of cytokine release is dose dependent and potentially correlated with PF-06755347 C_{max} and the rate of rise to achieve C_{max} . SC dosing of PF-06755347 offers the potential to blunt the severity of CRS by reducing the C_{max} and delaying the time to achieve C_{max} (T_{max}). The observed C_{max} (0.895 $\mu\text{g/mL}$) at the proposed starting SC dose of 25 mg is approximately 5-fold lower than the observed mean C_{max} (4.7 $\mu\text{g/mL}$) achieved at the highest tolerated IV dose level of 0.3 mg/kg ([Table 6](#)), with a safety margin of 1263 for C_{max} and 345 for AUC_{168} . Observed C_{max} values in subsequent dose levels of 50 and 100 mg were of 1.37 and 2.64 $\mu\text{g/mL}$ respectively; approximately 3.5-fold and 1.8-fold lower than the values observed at the 0.3 mg/kg IV dose level. The SC dose level of 300 mg will only be explored when SC doses up to 200 mg levels are deemed to be safe and well tolerated and within the PK stopping limit criteria.

In order to support subcutaneous delivery of PF-06755347, a toxicology study (Study 14MA141, IB Section 5.3.7) in NHP was conducted with a single 250 mg/kg SC dose and the results showed that the drug was tolerated.

The dose for the optional Japanese SC Cohort 12, if conducted, will be the highest dose from Cohorts 7-11 that is found to be safe and well tolerated.

Table 7. Observed/Predicted Human Exposures and Safety Margins Following Single SC Administration of PF 06755347

Dose (mg) ^a	Human Exposure of Plasma PF-06755347		Safety Margin ^b	
	C _{max} (µg/mL)	AUC ₅₇₆ or AUC ₁₆₈ (SC) (µg·hr/mL)	C _{max}	AUC
25 mg SC ^c	0.895	98.5	1263	345
50 mg SC ^c	1.37	159	825	214
100 mg SC ^c	2.64	315	428	108
200 mg SC	5.28	630	214	54
300 mg SC	7.92	945	143	36

- Depending on the safety and PK data available, dose escalation may be adjusted to doses other than those outlined above while following dose progression and stopping rules outlined in [Section 6.6](#) and [Section 6.7](#).

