4.2.1.3.3. Subcutaneous Administration in Participants with ITP

The starting dose of the ITP cohorts will be dependent on the equivalent dose levels in healthy participants having been studied and been deemed to be safe and well tolerated.

The dose levels to be tested in participants with ITP may include SC doses of 25 mg, 50 mg or 100 mg. The observed mean C_{av} after administration of a single 25 mg SC dose in HP was 0.586 µg/ml. This C_{av} is approximately 2-fold higher than the C_{av} of 0.25 µg/ml for ≥90% receptor occupancy for human FcγR. Thus it is expected that the lowest proposed dose in participants with ITP in this study could have pharmacological activity after a single dose.

The starting dose for participants with ITP will be 25 mg based upon the safety and tolerability data in HP.

Dosing progression and escalation are outlined in [Section 6.6](#) and [6.7](#).

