24. Participants who are investigator site staff members directly involved in the conduct of the study and their family members, site staff members otherwise supervised by the investigator, or participants who are Pfizer employees, including their family members, directly involved in the conduct of the study.
25. Other acute or chronic medical or psychiatric condition including recent (within the past year) or active suicidal ideation or behavior or laboratory abnormality (including prothrombin time [PT]/international normalized ratio [INR], partial thromboplastin time [PTT], Ddimer, fibrinogen, hematology and ionogram) that may increase the risk associated with study participation or investigational product administration or may interfere with the interpretation of study results and, in the judgment of the investigator, would make the participant inappropriate for entry into this study.

Prior/Concomitant Therapy

26. Use of prescription or nonprescription drugs and dietary supplements within 7 days or 5 half-lives (whichever is longer) prior to the first dose of IP. As an exception, acetaminophen/paracetamol may be used at doses of ≤ 1 g/day. Limited use of nonprescription treatments that are not believed to affect participant safety or the overall results of the study may be permitted on a case-by-case basis following approval by the Sponsor.
27. Herbal supplements must have been discontinued at least 28 days prior to the first dose of investigational product.
28. Due to the potential for interference with vaccine efficacy, the last dose of an approved COVID-19 vaccine must be at least 28 days prior to dosing with PF-06755347.

Prior/Concurrent Clinical Study Experience:

29. Participation in a previous cohort in the current study.

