6.3. Pharmacokinetic Endpoints

Blood samples for PK analysis of PF-06755347 will be taken according to the Schedule of Activities given in the protocol.

The following PK parameters will be calculated for PF-06755347 from the concentration-time values using standard non-compartmental methods:

Table 1. Non-compartmental PK Parameters

| Parameter | Analysis Scale | PF-06755347 |
|----------------------------|----------------|-------------|
| C_{\max} | ln | D |
| C_{\max} (dn) | ln | D |
| T_{\max}^* | R | D |
| $t_{1/2}^*$ | R | D |
| AUC_{last} | ln | D |
| AUC_{last}^* (dn) | ln | D |
| AUC_{inf}^* | ln | D |
| AUC_{inf}^* (dn) | ln | D |
| CL^* | ln | D |
| V_{ss}^* | ln | D |

Key: A=analyzed using statistical model, D=displayed with descriptive statistics, ln=natural-log transformed, R=raw (untransformed), *=if data permits

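### Protocol Table 10 defines SC bioavailability F without a dose term, although the IV doses are mg/kg and the SC doses are fixed mg, so the formula gives wrong values and conflicts with the table's own clearance rows

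*Protocol*

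**What the plan says.** Table 10 in Protocol Section 9.5.1 states how each PK parameter is determined. Three rows matter here:

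- F (SC): "F = AUC_{inf,sc} / AUC_{inf,iv}"
- CL (IV): "Systemic Clearance $Dose/AUC_{inf}"
- CL/F (SC): "Dose/AUC_{inf}$ for SC route"

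The table also lists AUCinf (dn), which is AUCinf divided by dose, as a separate parameter. The plain AUCinf in the F row is therefore not dose-normalised in the table's own notation.

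The two routes are dosed in different units. For IV, Protocol 4.2.1.3.1 says "A body weight-based dosing approach (mg/kg) was used in this study for the IV cohorts", and Table 6 lists 0.01 to 1 mg/kg. For SC the doses are fixed amounts. Table 7 lists 25 to 300 mg, and Protocol 4.2.1.3.2 says "The SC dose level of 300 mg will only be explored when SC doses up to 200 mg levels" have been found safe, well tolerated and within the PK limits.

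Exclusion criterion 29 for healthy participants (Protocol 5.2) is "Participation in a previous cohort in the current study".

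SAP 6.3 introduces its Table 1 with "The following PK parameters will be calculated for PF-06755347 from the concentration-time values using standard non-compartmental methods". That table does not contain F, CL/F or Vz/F.

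**The concern.** A ratio of AUCs measures bioavailability only if both AUCs come from the same dose or each is divided by its dose. Here the doses are not matched by design, so the ratio as written mainly reflects which SC cohort is paired with which IV cohort. Every other row of Table 10 that needs the dose writes it out; the F row does not.

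The row also cannot be computed within a participant. Everyone receives one route only, so F has to compare groups. The table does not say which summary of each group is compared or which IV dose level is the reference.

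Followed literally, the reported F would be wrong and could be far above 1. Two programmers who chose different IV cohorts would report very different values. The study moved from IV to SC dosing, and F is a natural descriptive summary of that change.

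**Working it through.** **Algebra (no data needed).** From the clearance rows:

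F = CL ÷ (CL/F) = (Dose_iv/AUC_iv) ÷ (Dose_sc/AUC_sc) = (AUC_sc/AUC_iv) × (Dose_iv/Dose_sc)

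The F row is AUC_sc/AUC_iv. F as written divided by F implied is therefore Dose_sc/Dose_iv, and the two agree only when the mg doses are equal.

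**Inputs for the illustration.** The documents give no numeric F and no AUCinf, so the tabulated AUCs stand in.

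- IV AUC168, µg·hr/mL (Table 6): 1.41, 10.5, 45.2, 139, 281, 490 at 0.01, 0.03, 0.1, 0.3, 0.7, 1 mg/kg.
- Observed SC AUC, µg·hr/mL (Table 7): 98.5, 159, 315 at 25, 50, 100 mg.
- Body weight: no mean is given. 70 kg is assumed, with a range of 50 to 100 kg (Protocol 5.1 requires more than 50 kg).

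**Checks on the inputs against the protocol's own figures.**

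- Safety margins: 34000/139 = 244.6 (stated 245). 34000/98.5, 34000/159 and 34000/315 give 345.2, 213.8 and 107.9 (stated 345, 214 and 108).
- AUC window: the SC column of Table 7 is headed as either AUC576 or AUC168. Protocol 4.2.1.3.3 says the mean Cav "after administration of a single 25 mg SC dose in HP was 0.586" µg/mL. Since 98.5/168 = 0.586 and 98.5/576 = 0.171, the 25 mg value covers 168 h. The same window is assumed for 50 and 100 mg.

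**Against 0.3 mg/kg IV (21 mg at 70 kg).**

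| SC dose | F as written | Dose-corrected, 70 kg |
|---|---|---|
| 25 mg | 98.5/139 = 0.71 | (98.5/25)/(139/21) = 0.60 |
| 50 mg | 159/139 = 1.14 | (159/50)/(139/21) = 0.48 |
| 100 mg | 315/139 = 2.27 | (315/100)/(139/21) = 0.48 |

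Over 50 to 100 kg the corrected values run from 0.34 (100 mg SC, 50 kg) to 0.85 (25 mg SC, 100 kg).

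**Same answer through the clearance rows.** For 100 mg SC at 70 kg, CL = 21/139 = 0.151 L/h and CL/F = 100/315 = 0.317 L/h. Their ratio is 0.48, against 2.27 from the F row.

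**Dependence on the IV cohort, 100 mg SC.**

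| IV dose (mg/kg) | 0.01 | 0.03 | 0.1 | 0.3 | 0.7 | 1 |
|---|---|---|---|---|---|---|
| As written | 223 | 30.0 | 6.97 | 2.27 | 1.12 | 0.64 |
| Corrected, 70 kg | 1.56 | 0.63 | 0.49 | 0.48 | 0.55 | 0.45 |

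Over all 3 × 6 = 18 observed SC–IV pairs, F as written exceeds 1 in 12. Corrected at 70 kg it exceeds 1 in 3, all against 0.01 mg/kg (1.56 to 1.96).

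**Where the doses nearly match.** 50 mg equals 0.7 mg/kg at 50/0.7 = 71.4 kg. At 70 kg the two forms give 159/281 = 0.57 and 0.57 × 49/50 = 0.55, as the algebra predicts.

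**The case against.** The strongest objection is about weight. F is not among the endpoints in Protocol Section 3, which names CL/F and Vz/F, and Table 10 defines both of those correctly. The PK escalation limits in Section 6.7 use Cmax and AUC168. AUCinf (dn), CL and CL/F would be available alongside a wrong F, so the error is recoverable, and a pharmacokineticist would probably supply the dose anyway. All of this limits the consequence. It does not make the written definition right, and Section 9.5.1.1 plans to summarise the PK parameters if data allow, so F could be reported.

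Second, Section 9.5.1 qualifies its derivation by participant and treatment with a where-applicable clause, so the table does not strictly promise an individual F. That is fair. The exclusion criterion therefore shows that a between-group method must be stated; it is not a contradiction in itself.

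Third, the SAP describes an IV-only study and omits every SC parameter, so its silence is not a decision about F. That is also true, but it means nothing there corrects the row.

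Fourth, the numbers are illustrative. The 223 comes from an extreme pairing that no document proposes, and counting all 18 pairs equally is a convenience. AUC168 may truncate SC and IV profiles differently, and body weight is assumed. The corrected values are therefore not estimates of true bioavailability. The algebraic result needs none of these inputs, and the ratios as written need no body weight.

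**Conclusion.** The concern holds. The F row of Table 10 lacks a dose term and disagrees with the table's CL and CL/F rows by exactly Dose_sc/Dose_iv. No other text in the protocol or SAP corrects it.

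The size depends on the dose pair. It is negligible where the mg doses nearly coincide and nearly fivefold for 100 mg SC against 0.3 mg/kg (100/21 = 4.8 at 70 kg). The figures rest on AUC168 as a proxy for AUCinf, a 168 h window for 50 and 100 mg SC, and an assumed body weight; the inconsistency between the rows does not.

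Adding the dose does not settle the reference. Against 0.01 mg/kg the corrected ratio is still above 1 at 70 kg, and Protocol 4.2.1.1 describes non-linear clearance, so the choice of IV dose level matters.

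This should be fixed, but its reach is limited: F is descriptive, and no primary conclusion or escalation decision depends on it.

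**What to change.** In Table 10, replace the F (SC) definition with the ratio of geometric mean AUCinf (dn), SC over IV, where each participant's AUCinf is divided by the mg actually received. In a footnote, state that F is a between-group estimate because the cohorts are parallel, and name the IV dose level or levels used as reference. Another dose-corrected between-group estimator would also serve, provided it is written down.

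The cost is one table row and one footnote, with no new data and no change to dosing or safety rules. It should be done before database lock.
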